6.8.2 Neurologic Events

Please see [Table 6-3](#) for the management of adverse events related to neurological events. For subjects with suspected neurological events, samples may be collected for analysis after discussion with the Medical Monitor.

Table 6-3. Management of Adverse Events Related to Neurologic Events

Toxicity	Grade*	Instructions for Treatment Interruption and Restart
Neurologic Events	3**	
 • Interrupt tarlatamab until the event improves to grade ≤ 1 and administer corticosteroids per local practice • Resume tarlatamab no less than 72 hours after the initial observation of the grade 3 adverse event at one dose level below • Permanently discontinue if: 
 ◦ Initial grade 3 neurologic event does not improve to grade ≤ 1 within 7 days, OR ◦ Grade 3 neurologic event reoccurs at the lower dose level within 7 days of re-initiation
	4	
 • Permanently discontinue tarlatamab
	Seizure	
 • Interrupt tarlatamab, administer corticosteroids and anti-seizure medication per local practice • For restart, refer to grade 3 neurologic events above for dose level rules for re-instituting infusion. • Do not re-initiate tarlatamab until 7 days after the last seizure and after therapeutic levels of anti-seizure medication are likely to have been achieved. • Permanently discontinue if a second seizure occurs with re-initiation of tarlatamab at any dose

* Per CTCAE Guidelines Version 4.0

** For adverse events Grade ≤ 2 , please follow institutional guidelines for management.

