6.2.2.1.1 Dosage Adjustment

Subjects should continue on the same target dose of tarlatamab (not including the initial run-in dose and step dose(s)) throughout the study. The two exceptions are subjects who meet criteria for intra-subject dose escalation (see Section 6.2.2.1.4 for more details) and subjects who experienced a DLT or other intolerable tarlatamab-related adverse events but showing evidence of clinical benefit. These subjects will have an option to reduce the dose to the immediate next lower dose level shown to be safe and tolerable in the dose exploration part of the study, after discussion with the Amgen Medical Monitor. The study drug can be resumed once the adverse events recover to Grade 0-1 and the reintroduction of tarlatamab is deemed safe by the investigator, Medical Monitor, and GSO. The subjects must be informed of the risk of continuing on therapy. Each subject is only allowed one dose reduction. For adverse events related to CRS, neurological events, and pituitary dysfunction, please see Sections 6.8.1, 6.8.2, and 6.8.3, respectively for guidelines for dose adjustments.

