6.2.2.1.3 Rules for Withholding or Restarting

Tarlatamab should be withheld for any of the following:

- DLT
- Symptomatic hypophysitis (See Section 6.8.3)
- Criteria for conditional withholding of tarlatamab due to potential hepatotoxicity (Section 6.2.3)

Tarlatamab dosing can be resumed if the toxicities resolve to grade ≤ 1 or return to subjects' baseline values within 4 weeks. The restarting of therapy should be deemed safe by the investigator and medical monitor.

Subjects should not be restarted with tarlatamab if the following treatment-related adverse events occur:

- Any grade ≥ 4 adverse events except those not considered DLT as described in Section 6.2.1.2.2
- Grade 3 adverse event(s) that do not recover to Grade 0-1 within 4 weeks
- Any grade 3 adverse events that recur (with the exception of grade 3 laboratory parameters not considered clinically relevant or recurrent non-febrile grade 3 neutropenia which resolves with supportive care to grade ≤ 1 or returns to subjects' baseline values within 4 weeks)
- Criteria for permanent withholding of tarlatamab due to potential hepatotoxicity (Section 6.2.3)

For adverse events related to CRS, neurological events and pituitary dysfunction, please see Sections 6.8.1, 6.8.2, and 6.8.3 respectively for guidelines for withholding and restarting criteria to pause enrollment.

At any point during the study, enrollment will be paused at the occurrence of 2 or more Grade 4 or one or more Grade 5 IP related adverse events. DLRT will be reconvened to review the safety data and determine appropriate next step that may include but not limited to implementing safety/toxicity management, informing health authorities, voluntarily putting the clinical trial on hold, or proceeding with enrollment (note: following the occurrence of an enrollment pause and DLRT review, a subsequent enrollment pause will occur at the occurrence of 2 or more new Grade 4 or one or more Grade 5 IP

related adverse events; additionally, if a pause and a DLRT has already occurred and the appropriate safety/toxicity management for Grade 4 adverse events have already been implemented a subsequent enrollment pause may not occur).

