6.8 Support Care and Potential Risk Management Guidelines for Tarlatamab

6.8.1 Cytokine Release Syndrome (CRS)

CRS is clinically defined and may have various manifestations. There are no established diagnostic criteria. Signs and symptoms of CRS may include (Lee et al, 2014):

- **Constitutional:** fever \pm rigors, fatigue, malaise, myalgias, anorexia, arthralgias, nausea, vomiting, headache

- **Neurologic:** headache, mental status changes, confusion, delirium, word finding difficulty or frank aphasia, hallucinations, tremor, dysmetria, altered gait, seizures
- **Respiratory:** dyspnea, tachypnea, hypoxemia
- **Cardiovascular:** tachycardia, hypotension, widened pulse pressure, increased cardiac output (early), potentially diminished cardiac output (late)
- **Gastrointestinal:** nausea, vomiting, diarrhea
- **Renal:** azotemia
- **Hepatic:** transaminitis, hyperbilirubinemia
- **Hematology/Coagulation:** hypofibrinogenemia ± bleeding, elevated D-dimer
- **Skin:** rash

CRS is an identified risk of tarlatamab administration. Subjects may be at an increased risk for CRS during the first few days following the initial infusion of tarlatamab and after a dose step increase. CRS may be life-threatening or fatal. Infusion reactions may be clinically indistinguishable from manifestations of CRS. Subjects will be hospitalized for intensive monitoring for 48 hours post tarlatamab infusion during all cycle 1 doses (refer to Section 8.1.2 for hospitalization guidance). Throughout the infusion with tarlatamab and at least 4 hours after the end of infusion, monitor subjects intensively for clinical signs (eg, fever, hypotension, tachycardia, dyspnea, tremors) and laboratory changes (eg, transaminase increase) which may be related to CRS.

Grading and management of CRS should be performed according to the guidelines provided in Table 6-2 (Lee et al, 2014). For subjects with suspected CRS, samples may be collected for analysis after discussion with the Medical Monitor.

Table 6-2. Grading and Management of Cytokine Release Syndrome

CRS Grade	Description of Severity ^a	Minimum Expected Intervention	Instructions for Dose Modifications of Tarlatamab

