3	
Symptoms require and respond to aggressive intervention
 
 • Oxygen requirement $\geq 40\%$, OR • Hypotension requiring high dose^b or multiple vasopressors, OR 
Grade 3 organ toxicity or grade 4 transaminitis per CTCAE criteria
	
Admit to intensive care unit for close clinical and vital sign monitoring per institutional guidelines.
 
Administer dexamethasone (or equivalent) IV at a dose maximum of 3 doses of 8 mg (24 mg/day). The dose should then be reduced step-wise.
 
Investigators should consider use of tocilizumab^{c,d} 8 mg/kg over 1 hour (not to exceed 800 mg). Repeat tocilizumab^{c,d} every 8 hours as needed if not responsive to IV fluids or increasing supplemental oxygen. Maximum of 3 doses in a 24-hour period. Maximum total of 4 doses.
 
If tocilizumab is not available, siltuximab (an anti-IL-6 monoclonal antibody) may be used. The recommended dose of siltuximab is 11 mg/kg administered over 1 hour as an intravenous infusion, consistent with the prescribing information for the treatment of multicentric Castleman's disease (Sylvant Prescribing Information), and the CARTOX Working Group Guidelines for CRS management (Neelapu et al, 2018). Siltuximab may be repeated if needed, in the event that CRS recurs after a subsequent infusion of tarlatamab. Siltuximab may not be repeated in an individual subject who develops anaphylaxis to siltuximab, or gastrointestinal perforation after siltuximab.
 
Investigators may also consider additional therapy, based on clinical judgment.
	
If CRS occurs during tarlatamab treatment, immediately interrupt tarlatamab and delay the next dose until event resolves to CRS grade ≤ 1 for no less than 72 hours.
 
Resume tarlatamab to next lower dose (continuation at same dose with dexamethasone premedication may be allowed after discussion with the medical monitor).
 
Permanently discontinue tarlatamab if there is no improvement to CRS \leq grade 2 within 5 days or CRS \leq grade 1 within 7 days.
 
Permanently discontinue tarlatamab or reduce to the next lower dose if CRS grade 3 occurs at the initial run in dose (ie, at MTD1) (applicable only after MTD1 has been defined).

CRS Grade	Description of Severity ^a	Minimum Expected Intervention	Instructions for Dose Modifications of Tarlatamab

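### Protocol Table 6-3 gives opposite instructions for a first seizure of Grade 4: a permanent stop in the Grade 4 row, possible restart after 7 days in the ungraded Seizure row

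*Protocol*

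**What the plan says.** **Table 6-3 (Protocol 6.8.2).** The Grade 4 row reads "Permanently discontinue tarlatamab" and makes no exception. The Seizure row carries no grade. It calls for interruption with corticosteroids and anti-seizure medication, then says "Do not re-initiate tarlatamab until 7 days after the last seizure", with the added condition that anti-seizure drug levels have probably become therapeutic. It takes its dose-level rule from the Grade 3 row (one level below) and requires a permanent stop only if a second seizure follows re-initiation. The Grade 3 row requires a permanent stop if the first event does not improve to Grade 1 or lower within 7 days, or if a "Grade 3 neurologic event reoccurs at the lower dose level within 7 days of re-initiation".

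**General rules (Protocol 6.2.2.1.3 and 6.2.2.1.1).** Section 6.2.2.1.3 bars restart after treatment-related events of Grade 4 or higher, apart from those not counted as dose-limiting toxicities (DLTs) under a Section 6.2.1.2.2. It also bars restart after "Any grade 3 adverse events that recur", with exceptions only for certain laboratory values and non-febrile neutropenia. Section 6.2.2.1.1 adds: "Each subject is only allowed one dose reduction". Both sections refer neurological events to 6.8.2.

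**CRS (Protocol 6.8.1).** The neurologic signs of CRS include "hallucinations, tremor, dysmetria, altered gait, seizures". For Grade 3 CRS, Table 6-2 says to "immediately interrupt tarlatamab and delay the next dose until event resolves to CRS grade" 1 or lower for at least 72 hours. Treatment then resumes at the next lower dose. The same dose is possible with dexamethasone premedication after discussion with the medical monitor.

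**The concern.** A site looking up a subject's first seizure in Table 6-3 finds two rows that fit if the event is Grade 4. One ends treatment and the other sets conditions for resuming it. Two sites could each follow the protocol and do opposite things.

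This is first a question of subject safety, and then one of data. Safety and tolerability is a primary objective. SAP 9.6.2 tabulates adverse events leading to withdrawal of tarlatamab separately from those leading to interruption, and SAP 9.6.8 summarizes number of doses, cumulative dose and relative dose intensity. The same event would enter different rows of these summaries depending on which line of Table 6-3 the site read.

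**Working it through.** No figure in the plan is in dispute, so the check sets the rules side by side.

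**Step 1. First seizure, by grade, under Table 6-3 alone**

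| First seizure | Grade row | Seizure row | Do they agree? |
|---|---|---|---|
| Grade 3 | Restart from 72 hours after first observation, one level below | Restart from 7 days after the last seizure, one level below | Yes: the Seizure row borrows only the dose-level rule and sets its own clock |
| Grade 4 | Permanent stop | Restart possible from 7 days; permanent stop only at a second seizure | No: opposite outcomes |

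**Step 2. Does 6.2.2.1.3 settle the Grade 4 case?** Its bar on restart points the same way as the Grade 4 row, but does not settle the matter, for two reasons.

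- The exception cites 6.2.1.2.2. The current text has no such section; the DLT definition is at 6.2.1.2.1. If that section is meant, its listed exclusions are fatigue (at Grade 3), certain non-febrile neutropenia, certain laboratory and electrolyte abnormalities, lymphopenia, fever, and tumor lysis syndrome with its manifestations. Seizure is not named.
- The same section sends neurological events to 6.8.2 for withholding and restarting. The question therefore returns to the table that contains the conflict.

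**Step 3. Grade 3 seizure within CRS.** Because 6.8.1 lists seizures as a CRS sign, such an event can be read as Grade 3 organ toxicity in Table 6-2.

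- Table 6-2: next dose after at least 72 hours at CRS Grade 1 or lower; lower dose, or the same dose under the stated conditions.
- Table 6-3: at least 7 days after the last seizure; one dose level below.

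Neither section says which table governs. As an illustration with assumed dates, take a seizure on day 5 of cycle 1 that resolves to Grade 1 or lower that day, with the next dose due on day 8:

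- Table 6-2: 5 + 3 = day 8, so the dose is permitted on schedule.
- Table 6-3: 5 + 7 = day 12, so the dose is 12 − 8 = 4 days late, or 4 × 24 = 96 hours.

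Section 4.2.1 lets a subject be replaced after a delay of more than 72 hours for reasons other than DLT during the DLT period. Section 9.3.1 requires treatment as planned in cycle 1 for a subject without a DLT to be evaluable. If this event is not a DLT, the choice of table could change evaluability in Part 1.

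**Step 4. Late recurrence of a Grade 3 neurologic event.** Table 6-3 requires a stop for recurrence within 7 days of re-initiation and says nothing about later recurrence. Under every-2-week dosing the rule covers 7 of the 14 days between doses. In cycle 1, with doses on days 1, 8 and 15, it covers the whole 7-day interval. The referrals to 6.8.2 in 6.2.2.1.1 and 6.2.2.1.3 do not say whether it replaces the general recurrence bar and the one-reduction limit or adds to them.

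**The case against.** The best defense is that most of the text on Grade 4 events points one way. The Grade 4 row, the Grade 4 CRS row of Table 6-2 and the bar in 6.2.2.1.3 all lead to a permanent stop, so the Seizure row merely omits its grade limit. That makes the omission easy to see, but does not remove it. A specific, ungraded row can equally be read as overriding a general one, and it gives its own condition for a permanent stop.

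A second defense is central oversight. Restart after Grade 2 or 3 CRS requires consultation with the medical monitor, and 6.2.2.1.3 requires the investigator and medical monitor to deem restart safe. This lowers the chance of sites diverging. It does not tell the medical monitor which row applies.

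Several stronger readings are tempting, but the documents do not support them:

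- **That every seizure faces three incompatible rules (72 hours, 7 days, never).** The 72-hour limit reaches a seizure only through CRS, and in Table 6-2 it runs from improvement to Grade 1 or lower. Both limits are minimum waits, so a site that waits 7 days can satisfy both. They are differing permissions without a ranking.
- **That the double-asterisk footnote contradicts the Seizure row for low-grade seizures.** Its marker is on the Grade 3 entry. It refers management of Grade 2 or lower events to institutional guidelines and gives no restart time or dose.
- **That Table 6-3 permits restart after a late recurrence while 6.2.2.1.3 forbids it.** Table 6-3 is silent. If the general rule fills the silence, there is no conflict.

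**Conclusion.** The contradiction within Table 6-3 stands: for a subject whose first seizure is Grade 4, the earliest restart is either never or 7 days after the last seizure. This rests only on the Seizure row carrying no grade. Section 6.2.2.1.3 does not resolve it, because its cross-reference is broken and it defers to 6.8.2.

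The CRS overlap is a real but lesser gap: two tables with different waits and dose options, and no stated precedence. The late-recurrence point is minor and is a matter of unclear precedence.

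How often any of this would arise cannot be estimated. The documents report that neurological events occurred in the first-in-human study but give no seizure rate. A reader might take the 31 of 70 monotherapy subjects (44.3%) with CRS in that study as the size of the overlap. That figure covers all grades. The scenario here needs Grade 3 CRS, which occurred in 1 of 70 (1.4%), with none of Grade 4 or higher at that cutoff. The case for acting rests on a safety instruction that contradicts itself and is cheap to correct, not on an expected large effect on the results.

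**What to change.** Reconcile the passages as follows:

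- In Table 6-3, state which grades the Seizure row covers, so that it, the Grade 4 row and 6.2.2.1.3 give one answer for a first Grade 4 seizure.
- In 6.2.2.1.3, correct the reference to 6.2.1.2.2.
- In 6.8.1 and 6.8.2, state which table governs a neurologic event that occurs as part of CRS.
- State whether 6.8.2 replaces or supplements the recurrence bar in 6.2.2.1.3 and the one-reduction limit in 6.2.2.1.1, and cover Grade 3 recurrence beyond 7 days.

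Which clinical rule is right in each case is for the sponsor's clinical team. The cost is protocol wording in the tables and cross-references concerned. It needs no new assessments and no change to the sample size.

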6.8.3 Pituitary Dysfunction

Based on the expression of DLL3 in the pituitary and observations in the cynomolgus monkey toxicology studies, there is a key risk of pituitary dysfunction in humans with administration of tarlatamab.

[figure not shown]
Early recognition of signs and symptoms and prompt intervention are essential.

Symptoms may derive from hormonal deficiencies and by the mass effect due to the swelling of the gland. The most common presentation includes headaches, asthenia, fatigue, nausea, weakness, lethargy, erectile dysfunction, and loss of libido.

The diagnosis and management of pituitary gland dysfunction should be performed according to the guidelines provided in [Figure 6-1](#). Cortisol, thyroid stimulating hormone (TSH), free thyroxine (FT4), follicle stimulating hormone/luteinizing hormone (FSH/LH), and testosterone will be evaluated at baseline and monitored throughout the study.

Adrenocorticotrophic hormone (ACTH), prolactin, and insulin-like growth factor 1 (IGF-1) will also be evaluated only at baseline and at the end of therapy. If any indications of pituitary gland dysfunction arise, a complete set of pituitary hormone panel will be evaluated, an endocrinologist will be consulted, and an MRI of the brain/pituitary will be conducted. After a confirmed diagnosis, tarlatamab will be withheld and corticosteroids and hormone replacement administered if clinically indicated. Please see [Figure 6-1](#) for guidelines for restarting tarlatamab. This management recommendation may be revised based on emerging clinical data.

Figure 6-1. Monitoring and Management of Pituitary Gland Dysfunction (Gonzalez et al, 2016)

6.8.4 Covid-19 Management

Grade	Interruption/ Delay	Specific Management	Re-start guidance	Permanent Discontinuation
SARS CoV2 infection and COVID19 disease				
asymptomatic	Interruption required until at least 10 days since positive SARS-COV-2 test UNLESS patient previously fully vaccinated against SARS-COV-2. If patient previously vaccinated and tests positive, then discuss with Medical Monitor.	Follow local guidelines and standard of care for COVID-19 treatment and isolation Contact Amgen Medical Monitor within 1 business day to ensure appropriate documentation & management of study activities	
 • Re-start possible upon agreement between Investigator and Amgen Medical Monitor provided: 
 ○ There are no new findings on physical exam related to SARS-COV-2, AND ○ Subject tests negative for SARS-COV-2 by RT-PCR ○ Consider CT of the chest imaging & EKG, ECHO and cardiology assessment prior to re-start of IP. 
OR
 
If subject continues to test positive for SARS-COV-2 more than 10 days after initial positive test, or if subject initially tests positive in the setting of prior COVID vaccination, resume IP only after discussion with patient and reassessment of individual risk/benefit & perform Ct of chest imaging & EKG (required) prior to re-start of IP. Consider ECHO and cardiology assessment
 
 • Consider hospitalization for re-start of IP based on length of treatment interruption, risk of CRS at restart, and amount of time since patient was last treated • Dose modification: resume at the same dose or reduce to next lower dose if clinically indicated 	
Immediately stop the infusion (if applicable) and permanently discontinue IP therapy IF:
 
Subject required treatment interruption greater than 28 days and upon discussion with Amgen Medical Monitor the decision is made to permanently discontinue treatment
 
OR
 
Initial benefit/risk assessment for individual patient is not maintained any longer

Grade	Interruption/ Delay	Specific Management	Re-start guidance	Permanent Discontinuation
SARS CoV2 infection and COVID19 disease				
			
 Premedication and assessments: follow guidance in SOC tables 	
symptomatic	Interruption required until at least 10 days since complete resolution of acute symptoms	
Follow local guidelines and standard of care for COVID-19 treatment and isolation
 
Contact Amgen Medical Monitor within 1 business day to ensure appropriate documentation & management of study activities
	
 Re-start possible upon agreement between Investigator and Amgen Medical Monitor provided: 
 There are no new findings on physical exam and chest imaging, related to SARS-COV-2 Subject tests negative for SARS-COV-2 by RT-PCR Consider CT of the chest imaging & EKG, ECHO and cardiology assessment prior to re-start of IP. OR 
 If subject continues to test positive for SARS-COV-2 more than 10 days after initial positive test, resume IP only after discussion with patient and reassessment of individual risk/benefit & perform Ct of chest imaging & EKG (required) prior to re-start of IP. Consider ECHO and cardiology assessment Consider hospitalization for re-start of IP based on length of treatment interruption, risk of CRS at restart, and amount of time since patient was last treated Dose modification: resume at the same dose or reduce to next lower dose if clinically indicated 	
Immediately stop the infusion (if applicable) and permanently discontinue IP therapy IF
 
Subject required treatment interruption greater than 28 days due to severe or life-threatening COVID-19
 
OR
 
Initial benefit/risk assessment for individual patient is not maintained any longer

Grade	Interruption/ Delay	Specific Management	Re-start guidance	Permanent Discontinuation
SARS CoV2 infection and COVID19 disease				
			
• Premedication and assessments: follow guidance in SOA tables	

6.8.5 Tumor Lysis Syndrome (TLS)

Tumor lysis syndrome, a preventable complication of cancer therapies, is a result of rapid tumor necrosis with release of intracellular ions into the bloodstream. It is characterized by hyperuricemia, hyperkalemia, and hyperphosphatemia. TLS occurs primarily in hematological malignancies and high-grade lymphomas. The occurrence of TLS in solid tumors is rare but is more common in highly responsive tumors with large tumor burdens. Pretreatment elevation of serum lactate dehydrogenase (LDH) and uric acid, and pre-existing renal failure are risk factors for the development of TLS (Kallab and Jillella, 2001). In light of the extremely low incidence of TLS in patients with solid tumors, routine prophylactic measures, such as allopurinol and alkaline hydration, cannot be recommended in all patients. However, the potential for TLS in patients with large tumor burdens who present with renal insufficiency, dehydration, hyperuricemia, and elevated serum LDH levels must be recognized, to allow for appropriate monitoring after treatment and early initiation of therapeutic measures if necessary (Kalemkerian et al, 1997). Prophylaxis with IV hydration 1 L normal saline over 4 to 5 hours immediately following all dose(s) in cycle 1 is required. Careful monitoring of fluid status and additional IV hydration as clinically appropriate is recommended. Allopurinol or rasburicase can be considered for both prophylaxis and/or treatment of hyperuricemia.

